2.3.3 Decitabine

Decitabine is known to be well tolerated, with a favorable extramedullary toxicity profile and infrequent treatment-related mortality. Decitabine is a nucleoside analog that is unsuitable for methylation due to the replacement of carbon with nitrogen at the 5' position of the pyrimidine ring. Decitabine is activated intracellularly by deoxycytidine kinase and other nucleotide kinases to the active metabolite 5-aza-2'-deoxycytidine-triphosphate (5-aza-2' -dCTP) that can be

PROTOCOL TITLE: I 49217 - Phase 1 CDX-1401/ Poly-ICLC +Decitabine +Nivolumab in
Patients with MDS or Low Blast Count AML

incorporated into DNA during the S-phase of the cell cycle and forms irreversible covalent bonds with DNA methyltransferases (DNMT) at cytosine sites targeted for methylation (32). Decitabine is believed to exert its antineoplastic effects by inhibition of DNA methyltransferases, causing DNA hypomethylation and activation of genes involved in differentiation or apoptosis. Decitabine was the first drug to demonstrate significant activity against MDS and has been shown to induce transfusion independence for red blood cells and platelets as well as improvements in neutropenia (47).

Based upon these results decitabine was approved by the US food and drug administration for all MDS subtypes in 2006 and it remains a frequent standard approach to the treatment of patients with MDS (2). It has been hypothesized that low dose, prolonged exposure to decitabine correlates with clinical response as a result of changes in gene expression induced by a reduction in DNA methylation; rather than cytotoxicity which occurs with higher doses of decitabine (48). Recently we and others have shown that exposure of myeloid cells to decitabine and azacitidine (an analog of decitabine which incorporates into both DNA and RNA), can induce expression of CT antigens when given in vitro to AML cell lines, and further that patients treated with these drugs can induce expression of some CT antigens as well (17, 18, 49).

2.4 Rationale

The hypomethylating agents (HMAs) azacitidine and decitabine are the standard of care for the treatment of myelodysplastic syndromes (MDS) but only about 40% of patients respond. We have demonstrated that AML/MDS patients receiving HMAs express the immunogenic tumor antigen NY-ESO-1 in circulating CD34+ blasts after treatment in both clinical responders and non-responders. These data provided the rationale for our recently completed phase I study combining NY-ESO-1 vaccination with decitabine in newly diagnosed MDS patients. Nine patients, all at the Roswell Park Cancer Institute, were enrolled and treated on our study. A majority of the treated patients developed NY-ESO-1 specific T-cells in response to vaccination, but these were less robust than the responses observed in patients with solid tumors who got the same vaccine. We and others have shown that PD-L1 is expressed on myeloid cells from patients with MDS and AML (7, 9) and further, that that expression of the immune checkpoint protein PD-1 is induced in lymphocytes from AML/MDS patients receiving decitabine. Based on these results, we propose a Phase 1 study that adds the PD-1 inhibitor nivolumab to our backbone combination of standard-dose decitabine and NY-ESO-1 vaccination in HMA naïve, non-transplant eligible, MDS patients and low blast count AML patients. We will test the hypothesis that the addition of nivolumab will improve the qualitative and quantitative antigen specific CD4+ and CD8+ T-cell response to NY-ESO-1 vaccination in MDS/AML patients.

3 INCLUSION AND EXCLUSION CRITERIA

3.1 Inclusion Criteria

Subjects who present with a suspected or confirmed diagnosis of MDS/AML, and who are interested in potential participation on a clinical trial, will be screened for enrollment. Only patients who are willing to sign a written informed consent form will be screened. Patients must undergo bone marrow aspirate and biopsy with sample acquisition for protocol screening.

To be included in this study, participants must meet the following criteria:

1. Have a confirmed diagnosis of:

PROTOCOL TITLE: I 49217 - Phase 1 CDX-1401/ Poly-ICLC +Decitabine +Nivolumab in
Patients with MDS or Low Blast Count AML

- a. IPSS intermediate-1, intermediate-2 or high-risk MDS including Chronic Myelomonocytic Leukemia (CMML) **OR**
 - b. Low blast count AML with $\leq 30\%$ blasts previously classified as Refractory Anemia with excess blasts in transformation.
2. Age ≥ 18 years of age.
 3. Have an ECOG Performance Status of ≤ 2 . Refer to **Appendix C**.
 4. Have adequate organ function defined by the following laboratory values:
 - Hepatic:
 - Total bilirubin ≤ 3 X upper limit of normal (ULN) (except subjects with Gilbert Syndrome, who can have total bilirubin up to 3.5 X ULN)
 - Aspartate Transaminase (AST/SGOT) and Alanine Transaminase (ALT/SGPD) ≤ 3 X ULN
 - Renal:
 - Serum creatinine ≤ 2.5 X ULN
 - Cardiac:
 - Troponin-I, CK-MB \leq ULN
 - LVEF \geq LLN (institutional limit)
 5. Participants of child-bearing potential must agree to use adequate contraceptive methods (e.g., hormonal or barrier method of birth control; abstinence) prior to study entry. Should a woman become pregnant or suspect she is pregnant while she or her partner is participating in this study, she should inform her treating physician immediately.
 6. Participant or legal representative must understand the investigational nature of this study and sign an Independent Ethics Committee/Institutional Review Board approved written informed consent form prior to receiving any study related procedure.
 7. No prior exposure to nivolumab.
 8. No prior investigational therapy within 2 weeks prior to study enrollment.

Refer to **Appendix A** for the **ELIGIBILITY VERIFICATION FORM: INCLUSION CRITERIA** checklist.

3.2 Exclusion Criteria

Because this study is designed to examine survival as a secondary endpoint we will exclude patients who are eligible for an allogeneic bone marrow transplant at the time of study enrollment. If an enrolled patient subsequently becomes eligible for transplant, they will not be prevented from proceeding to the appropriate clinical treatment indicated.

Participants will be excluded from this study for the following:

1. Subjects with life-threatening illnesses other than MDS, uncontrolled medical conditions or organ system dysfunction which, in the investigator's opinion, could compromise the subject's safety, or put the study outcomes at risk.
2. AML associated with inv(16); t(16;16); t(8;21) or t(15;17).

PROTOCOL TITLE: I 49217 - Phase 1 CDX-1401/ Poly-ICLC +Decitabine +Nivolumab in
Patients with MDS or Low Blast Count AML

3. Previously untreated MDS with isolated del5q (for which lenalidomide is approved an approved therapy) and chronic myelomonocytic leukemia (CMML) with rearrangements of the PDGF receptor (for which imatinib is approved therapy), unless they have previously failed these approaches.
4. Subjects with symptomatic central nervous system (CNS) disease which is not adequately controlled.
5. Subjects who have received prior radiation therapy for extramedullary disease within 2 weeks of first dose.
6. Has known immunosuppressive disease (e.g. HIV, AIDS or other immune depressing disease). Testing is not required, only to be done for a possible diagnosis which is not confirmed.
7. Uncontrolled intercurrent illness including, but not limited to, ongoing or active infection, symptomatic congestive heart failure, unstable angina pectoris, cardiac arrhythmia, or psychiatric illness/social situations that would limit compliance with study requirements. In addition, subjects will be excluded for any of the following:
 - Myocardial infarction or arterial or venous thromboembolic events within 6 months prior to baseline or severe or unstable angina, New York Heart Association (NYHA) Class III or IV disease
 - Active congestive heart failure (New York Heart Association functional classification III or IV).
 - Documented history of cardiomyopathy with EF < 30%.
 - Uncontrolled hypertension (SBP > 160/DBP > 100 despite medical intervention).
 - History of myocarditis of any etiology
8. Subjects who have hypersensitivity to decitabine, CDX-1401, poly-ICLC or nivolumab.
9. History of auto-immune disease (e.g., thyroiditis, lupus), except vitiligo.
10. Pregnant or nursing female subjects.
11. Unwilling or unable to follow protocol requirements.
12. Any condition which in the Investigator's opinion deems the participant an unsuitable candidate to receive study drug.
13. Regular use of immunosuppressant drugs such as steroids (>20mg prednisone equivalents), azathioprine, tacrolimus, cyclosporine, etc. Use is not permitted within 4 weeks before recruitment.

Refer to **Appendix B** for the **ELIGIBILITY VERIFICATION FORM: EXCLUSION CRITERIA** checklist.

3.3 Special Populations

Only adult patients who are able to provide informed consent will be eligible. Adult patients without capacity, infants and children will be excluded. No pregnant women or prisoners will be eligible for enrollment on this study.

PROTOCOL TITLE: I 49217 - Phase 1 CDX-1401/ Poly-ICLC +Decitabine +Nivolumab in Patients with MDS or Low Blast Count AML

3.4 Inclusion of Women and Minorities

Both men and women and members of all races and ethnic groups are eligible for this study.

4 LOCAL AND STUDY-WIDE NUMBER OF SUBJECTS

A maximum of 18 evaluable participants (minimum of 3) at multiple sites, including RPCI will be enrolled and treated on this study.

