9.1 Study Design

The primary objective of this Phase I study is to determine safety of the combinatorial regimen. The secondary objective is to assess immune and molecular epigenetic response. An exploratory

PROTOCOL TITLE: I 49217 - Phase 1 CDX-1401/ Poly-ICLC +Decitabine +Nivolumab in Patients with MDS or Low Blast Count AML

objective will be to record the response rate (including Complete Response (CR), Partial Response (PR) and Hematological Improvement (HI)) in the enrolled patients who will have a diagnosis of MDS or low blast count AML patients in order to provide descriptive characteristics.

This is a modified 3+3 design with a 12 patient expansion cohort at the maximum tolerated dose (MTD) or the maximum administered dose (MAD). We expect 18 patients to be enrolled (all at Dose Level +1), given experience with these treatments in other studies.

Three patients will be accrued at dose level 1. If 0 or 1 of the first 3 patients has a dose limiting toxicity (DLT, defined in section 10), then 3 more patients will be enrolled at the same dose. If a maximum of 1 of these six patients has a DLT, dose level 1 will be declared the maximum administered dose (MAD) and an additional 12 patients will be enrolled in an expansion cohort. Dose level +1 is considered the most likely MAD, given the low observed toxicity rates with NY-ESO-1 vaccine therapy. If the true DLT rate is 20%, there is an 85% probability of ending the trial with these 18 patients. Observed toxicity rates associated with NY-ESO-1 treatment have been below 20%. The accrual decision rules are shown in Table 4.

If either of the DLT thresholds at dose level 1 is exceeded, the same rules will be followed for dose level -1. If more than one third of patients at dose level -1 have a DLT, the study will be terminated.

Table 4 Dose De-Escalation Plan

Dose Level	Number of Subjects with a Dose-Limiting Toxicity at a Given Dose Level	Escalation Decision Rule
DL 1	2,3 out of 3	De-escalate to Dose -1. Enroll 3 patients
	0,1 out of 3	Maintain Dose Level 1. Enroll three more patients
	0,1 out of 6	Declare Dose Level 1 the maximum administered dose (MAD). Enroll expansion cohort of 12 additional patients.
	≥2 out of 6	De-escalate to Dose -1. Enroll 3 patients
DL -1	2,3 out of 3	Stop the study
	0,1 out of 3	Maintain Dose Level -1. Enroll three more patients
	0,1 out of 6	Declare Dose Level -1 the maximum tolerated dose (MTD). Enroll expansion cohort of 12 additional patients.

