19.1 Sample Size Determination

A maximum of 18 evaluable participants will be enrolled in this study. The number of participants required is a function of the unknown relationship between this treatment combination and the toxicity rate. Accrual is expected to take 2-4 years. We expect 18 patients will be accrued, all at Dose Level 1.

The primary statistical endpoint is the proportion of n=12 evaluable patients in the expansion cohort experiencing a DLT. A DLT rate ≥ 0.60 is considered unacceptable.

The DLT rate will be estimated as a binomial proportion of evaluable patients with any DLT. If the upper 1-sided 95% Jeffreys credible interval exceeds 0.60, the protocol therapy will be considered too toxic. With n=12 evaluable patients, this occurs if 5 or more patients experience a DLT. With n=12 evaluable patients, the upper confidence limit is less than 0.60 in 80% of similar experiments when the true DLT rate is 0.27.

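### The stated limits of 18 maximum and 3 minimum contradict Table 4, which can need up to 24 patients and at least 6

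*Combined protocol and SAP*

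**What the plan says.** Section 4: "A maximum of 18 evaluable participants (minimum of 3) at multiple sites, including RPCI will be enrolled and treated on this study". Section 19.1: "A maximum of 18 evaluable participants will be enrolled in this study". The same paragraph of Section 19.1 also gives 18 as the expected number: "We expect 18 patients will be accrued, all at Dose Level 1".

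Section 9.1 and Table 4 set the accrual rules:

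- Dose level 1, first cohort: "Three patients will be accrued at dose level 1".
- 0 or 1 DLT in 3: "Maintain Dose Level 1. Enroll three more patients".
- 0 or 1 DLT in 6: "Declare Dose Level 1 the maximum administered dose (MAD). Enroll expansion cohort of 12 additional patients".
- 2 or 3 DLTs in 3, or 2 or more in 6: "De-escalate to Dose -1. Enroll 3 patients".
- Dose level -1 has the same 3-then-3 structure. After 0 or 1 DLT in 6: "Declare Dose Level -1 the maximum tolerated dose (MTD). Enroll expansion cohort of 12 additional patients". Table 4 allows the study to stop only at dose level -1.

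Section 19.1 defines the primary statistical endpoint on 12 evaluable expansion patients. The regimen is too toxic if the upper one-sided 95% Jeffreys limit exceeds 0.60, which the section says happens at 5 or more DLTs. It adds that the limit stays below 0.60 in 80% of similar experiments when the true rate is 0.27. No other expansion size is provided for.

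**The concern.** The figure of 18 equals 6 + 12, which is the total when dose level 1 is accepted. It leaves out the de-escalation path that Table 4 spells out. A study that de-escalates and then follows Table 4 must exceed the maximum stated in two sections. A study that respects the maximum cannot fill the expansion on which the primary endpoint is defined.

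The conflict arises only after DLTs at dose level 1, when the safety estimate matters most. Section 18.3 requires IRB approval before a revision is implemented, so repairing the number at that point would hold up the study.

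**Working it through.** **Step 1. Totals under Table 4.**

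| Path | Patients | Total |
|---|---|---|
| Dose level 1 accepted | 6 + 12 | 18 |
| Level 1 fails at 3, level -1 fails at 3 | 3 + 3 | 6 |
| Level 1 fails at 3, level -1 fails at 6 (or the reverse) | 3 + 6 | 9 |
| Both levels fail at 6 | 6 + 6 | 12 |
| Level 1 fails at 3, level -1 accepted | 3 + 6 + 12 | 21 |
| Level 1 fails at 6, level -1 accepted | 6 + 6 + 12 | 24 |

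The stated 18 reproduces for the first row only. The maximum is 24 and the minimum is 6.

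**Step 2. Chance of needing more than 18.** Assume independent patients and the same DLT rate p at both levels. A level is accepted with probability A = P(X ≤ 1 | n = 6, p), because at most 1 DLT in 6 implies at most 1 in the first 3. More than 18 are needed when level 1 fails and level -1 is accepted, so P(total > 18) = (1 − A) × A.

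At p = 0.20:
- A = 0.8⁶ + 6 × 0.2 × 0.8⁵ = 0.655, so de-escalation has probability 0.345.
- Failure within the first 3 has probability 3 × 0.2² × 0.8 + 0.2³ = 0.104. P(total = 21) = 0.104 × 0.655 = 0.068.
- Failure at 6 has probability 0.345 − 0.104 = 0.241. P(total = 24) = 0.241 × 0.655 = 0.158.
- The sum is 0.226.

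| DLT rate | P(total > 18) |
|---|---|
| 5% | 3.2% |
| 10% | 10.1% |
| 20% | 22.6% |
| 27% | 25.0% |
| 30% | 24.4% |

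A lower rate at level -1 raises these figures. With 20% at level 1 and 10% at level -1, where A = 0.886, the result is 0.345 × 0.886 = 30.5%.

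**Step 3. The primary rule at n = 12.** The Jeffreys upper limit is the 0.95 quantile of Beta(x + 0.5, n − x + 0.5). It is 0.569 at 4/12 and 0.648 at 5/12, so the cut-off of 5 reproduces. P(X ≤ 4 | 12, 0.27) = 0.798, which matches the stated 80%.

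**Step 4. The same rule if 18 is a hard cap.** The places left for expansion at level -1 are 18 − (3 + 6) = 9 or 18 − (6 + 6) = 6.

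| Expansion n | Largest passing count (limit) | Smallest failing count (limit) | P(pass) at 0.27 | P(pass) at 0.60 |
|---|---|---|---|---|
| 12 | 4 (0.569) | 5 (0.648) | 79.8% | 5.7% |
| 9 | 2 (0.492) | 3 (0.604) | 54.5% | 2.5% |
| 6 | 1 (0.495) | 2 (0.659) | 48.7% | 4.1% |

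For n = 6, the pass probability at 0.27 is 0.73⁶ + 6 × 0.27 × 0.73⁵ = 0.151 + 0.336 = 0.487. A truncated expansion is no more lenient at 0.60. What it loses is the ability to clear a regimen whose true rate is 0.27.

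**The case against.** The strongest reply is that 18 was meant as the expected number and that Table 4 governs. Sections 8.1, 9.1 and 19.1 all present 18 as what is expected, and Section 19.1 says the number required depends on an unknown toxicity relationship. On that reading the n=12 rule survives and only a number is wrong. This is plausible, and it makes the n = 9 and n = 6 results hypothetical. But Section 19.1 uses both maximum and expected for 18, and nothing says which prevails.

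The word evaluable does not rescue the cap. Section 19.5.1 counts everyone who receives any study treatment as evaluable for toxicity, and 18 already includes the six 3+3 patients.

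The 22.6% also depends on the rule. Section 9.1 claims an 85% chance of ending with 18 at a 20% DLT rate, which would leave at most 15% for anything larger. Table 4 gives 65.5%. Tolerating 2 DLTs in 6 at both levels gives 85.2%, and then P(total > 18) = 0.148 × 0.852 = 12.6%. Section 9.1's prose also words the stopping rule at level -1 differently from Table 4 (more than one third, against 2 or more in 6). Tolerating 2 in 6 there only gives 0.345 × 0.852 = 29.4%. So a range is more honest than a single figure, and those passages need reconciling in their own right. Under every one of these readings the maximum is still 24 and the minimum still 6.

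Two smaller points stand. Section 9.1 reports toxicity rates below 20% with NY-ESO-1 treatment, so the lower rows of the Step 2 table are relevant, although that experience is not with this triple combination. The minimum of 3 enters no analysis and could arise from termination under Section 18.4, so it is the lesser error.

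**Conclusion.** The concern holds. The maximum of 18 in Sections 4 and 19.1 contradicts Table 4, whose maximum is 24 evaluable patients before any replacements under Section 9.2. The minimum of 3 cannot be reached through the dose rules, whose minimum is 6. These limits follow by addition and need no assumption about toxicity.

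How often the conflict would arise does depend on assumptions. Under Table 4 with equal rates at both levels, it is about 3% to 25% over DLT rates of 5% to 30%. At 20%, the rate the protocol itself uses, it is 22.6%, or 12.6% to 29.4% under the other readings of the 6-patient threshold.

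If 18 binds, the primary analysis has no defined sample size or cut-off on those paths. If it does not bind, the stated size is too small by 3 or 6 on the same paths. A correction is needed because the sample-size statement and the decision table cannot both be followed.

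**What to change.** In Sections 4 and 19.1, state 18 as the expected number, 24 (6 + 6 + 12) as the maximum and 6 (3 + 3) as the minimum under the dose rules. Say that replacements under Section 9.2 come on top. Align Section 7, which plans its timeline around 18 patients.

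If 18 is meant as a hard cap, keep it, but amend Table 4 and Section 19.1 to give the reduced expansion at dose level -1 (9 or 6), its own cut-off (3 or more of 9, or 2 or more of 6, under the present Jeffreys criterion) and its own operating characteristics.

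The first option costs wording and a revised accrual number, and adds no patient that Table 4 does not already require. The second also costs precision in the primary estimate, as Step 4 shows. In the same amendment, reconcile the 85% statement and the one-third wording in Section 9.1 with Table 4.

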5 LOCAL AND STUDY-WIDE RECRUITMENT METHODS

- Potentially eligible patients will be recruited from the population of newly diagnosed MDS patients referred to the protocol investigators. Patients will have a suspected or known diagnosis of MDS or low blast count AML with MDS related changes and be appropriate for therapy with a hypomethylating agent (HMA).
- Patients will be referred to any of the leukemia doctors where the study is open and, will be offered the opportunity to enroll on protocol should they wish to do so. Information regarding this study will be conveyed to local hematologists who see patients with newly diagnosed MDS in a letter approved by the IRB.
- A letter will be distributed to local hematologists/oncologist who sees potentially eligible patients. These physicians can then refer patients to us for consideration of trial participation. The study will be registered on clinicaltrials.gov and RPCI will hold the IND for this study. Patients may review the study on this website or on the RPCI and MDACC external websites.
- All study related advertising documents used at any site will first be reviewed by the RPCI IRB and by the local IRB at any participating institution prior to their use.

6 MULTI-SITE RESEARCH

Refer to **Appendix K**: Instructions for Network Sites.

- The proposed project will be opened initially at Roswell Park Cancer Institute and at one potential additional site. In order to ensure that all patients are treated appropriately and in a consistent fashion we will ensure the following:
 - All sites will have the most current version of the protocol, consent document, and HIPAA authorization.
 - All required approvals (initial, continuing review and modifications) have been obtained at each site (including approval by the site's IRB of record).
 - All modifications have been communicated to sites, and approved (including approval by the site's IRB of record) before the modification is implemented.
 - All engaged participating sites will safeguard data, including secure transmission of data, as required by local information security policies.
 - All local site investigators will conduct the study in accordance with applicable federal regulations and local laws.

PROTOCOL TITLE: I 49217 - Phase 1 CDX-1401/ Poly-ICLC +Decitabine +Nivolumab in Patients with MDS or Low Blast Count AML

- All non-compliance with the study protocol or applicable requirements will be reported in accordance with local policy.
- This study will have up to two total sites including RPCI. If the study opens at a second site, the investigators will have a biweekly (i.e., once every 2 weeks) conference call to discuss the results of all patients enrolled and treated on study, otherwise the investigator will review the records of all patients enrolled at least every 2 weeks. At this review the principal investigators will review the following:
 - Problems (inclusive of reportable events).
 - Interim results.
 - The closure of the study according to the described stopping rules below
- As a phase 1 study, all AEs will be reviewed weekly by the Early Phase Clinical Trials committee at RPCI.

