7 STUDY TIMELINES

- During the 3+3 component, accrual will be suspended until the three patients in each cohort have completed the DLT window (6 weeks after the last patient has begun therapy).
- Patients will be enrolled and treated on study for as long as they are deriving clinical benefit. Treatment on study has no specified end time.
 - Median progression free survival for patients with MDS receiving hypomethylating agents on clinical trials is between 18 and 24 months.
 - This study is therefore likely to enroll all 18 patients within 2 years and all patients are likely to have completed the study within 7 years of study opening.
- An interim analysis of correlative studies will be performed after every 3 patients have been enrolled and treated on the study for at least 5 months or come off treatment, whichever comes first.
- Given the long half-life for nivolumab and the known risk of late presenting adverse events, patients enrolled and treated on study will be followed for AEs for 180 days after the last dose of nivolumab.
- Patients will stay on study for 5 years after the last patient has been enrolled or until disease progression, whichever occurs first.

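### At dose level 1 no numeric rule suspends expansion accrual, although with 12 in the denominator the 5th DLT already meets the plan's own criterion for too toxic

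*Combined protocol and SAP*

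**What the plan says.** Section 6 lists, among the items for the two-weekly investigator review, "The closure of the study according to the described stopping rules below". The numeric rules that come after it are in Section 9.1. Table 4 sets DLT counts for the first 3 and first 6 patients at each dose level. Once a level is declared, its instruction is "Enroll expansion cohort of 12 additional patients", with no DLT check inside that cohort. A separate sentence in Section 9.1 ends the study when over a third of the patients at dose level -1 have had a DLT; dose level 1 has no counterpart.

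Section 7 limits the pause in accrual: "During the 3+3 component, accrual will be suspended until the three patients in each cohort have completed the DLT window". Section 10.3 adds one hold before the expansion opens, to watch for late toxicity. The interim analyses in Section 7 concern correlative studies.

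Section 19.1 states what the expansion is to measure: "The primary statistical endpoint is the proportion of n=12 evaluable patients in the expansion cohort experiencing a DLT". It then sets the level against which the result is judged: "A DLT rate ≥ 0.60 is considered unacceptable". The decision rule follows from an interval: "If the upper 1-sided 95% Jeffreys credible interval exceeds 0.60, the protocol therapy will be considered too toxic". Section 19.1 converts this to a count: "With n=12 evaluable patients, this occurs if 5 or more patients experience a DLT". It attaches no accrual action to that count.

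**The concern.** The criterion is read once, on 12 patients, but can be settled sooner. When a fifth expansion patient has a DLT, the remaining patients cannot bring the result back under 0.60 as long as the denominator is 12. The plan would still let the cohort fill. Section 10.3 defines a DLT as a related non-hematologic grade 4 or 5 event, so those entering after the fifth would start a regimen that the plan's own rule has already rejected after five such events. Their data could not change the verdict, although they would sharpen the estimate. Section 6 points the reviewers to stopping rules, and the ones they will find say nothing about the expansion at dose level 1.

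**Working it through.** **Inputs.** From Section 19.1: n = 12, limit 0.60, upper one-sided 95% Jeffreys limit, count of 5, and the statement that "the upper confidence limit is less than 0.60 in 80% of similar experiments when the true DLT rate is 0.27". From Section 9.1, Table 4: the expansion opens after 0 or 1 DLTs in 6. From Sections 7 and 8.1: a DLT window from day -14 to cycle 2 day 1, about 6 weeks. Assumptions: independent patients with a common true DLT rate p, shown over a range. The enrolment lag is not given in the documents, so it is shown at 0 and 2 patients.

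**1. The plan's own figures.** The upper limit for x DLTs in n is the 0.95 quantile of Beta(x + 0.5, n − x + 0.5). At n = 12 it is 0.484 for 3, 0.569 for 4, 0.648 for 5 and 0.720 for 6. The boundary of 5 reproduces. P(X ≤ 4 | n = 12, p = 0.27) = 0.798, which reproduces the stated 80%.

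**2. Irreversibility.** The limit rises with x. Five DLTs with n = 12 give at least 0.648 whatever follows. At most 12 − 5 = 7 patients remain at that point.

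**3. Saving if the expansion opens.** The fifth DLT falls on patient k with probability C(k−1, 4) p^5 (1−p)^(k−5), for k = 5 to 12. The mean number spared is the sum of (12 − k) times this probability. With L patients already enrolled when the fifth DLT is known, 12 − k becomes max(0, 12 − k − L).

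**4. The gate.** P(0 or 1 of 6) = (1−p)^6 + 6p(1−p)^5. At p = 0.40 this is 0.0467 + 0.1866 = 0.233. Multiplying by the mean spared with L = 0 gives the saving as seen from study start at dose level 1, for example 0.233 × 1.42 = 0.33.

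| True DLT rate | 5th DLT before patient 12 | Mean spared, L = 0 | Mean spared, L = 2 | Gate passed | Spared from study start, L = 0 |
|---|---|---|---|---|---|
| 0.40 | 0.467 | 1.42 | 0.59 | 0.233 | 0.33 |
| 0.50 | 0.726 | 2.58 | 1.23 | 0.109 | 0.28 |
| 0.60 | 0.901 | 3.79 | 2.06 | 0.041 | 0.16 |

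Columns 2 to 4 are conditional on the expansion opening. With L = 2 the last column becomes 0.14, 0.13 and 0.08 (column 4 times column 5).

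**5. The full seven.** This needs DLTs in all of the first five expansion patients: p^5 = 1.0%, 3.1% and 7.8% at 0.40, 0.50 and 0.60, given that the expansion opens.

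**6. Effect on the verdict.** Stopping at the fifth DLT leaves P(too toxic) where it was: 0.202 at p = 0.27, 0.562 at 0.40, 0.806 at 0.50 and 0.943 at 0.60. At p = 0.20 the stop would come before patient 12 in only 5% of expansions.

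**7. Denominator.** Section 9.2 replaces expansion patients who leave before the end of cycle 4 for reasons other than toxicity, while Section 19.5.1 counts everyone treated as evaluable for toxicity. If replaced patients also count, 5 of 13 gives 0.610 (still too toxic) but 5 of 14 gives 0.575 (not).

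**8. Feasibility.** Section 19.1 expects accrual over 2 to 4 years. For 18 patients that averages one per 24/18 = 1.3 to 48/18 = 2.7 months, against a window of about 6 weeks. The average includes the 3+3 pauses, so the expansion may run faster.

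**The case against.** The strongest reply is that the 3+3 part does most of the protecting. At the rates where early stopping would help most, the expansion seldom opens, so the expected saving from study start is a fraction of a patient. That stands, and it sets the size of the point. It does not remove the gap, because the gate can be passed by chance and the rule matters once it has been.

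Three stronger readings are tempting, and the documents do not support them.

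- A reader might infer that seven patients would typically be treated after the answer is known. Seven is an upper bound and is rare. It also presumes that every outcome is known before the next entry, whereas the expansion has no pauses and a window of about 6 weeks.
- A reader might infer that nothing at all could stop accrual. Section 6 provides two-weekly investigator review and weekly AE review, Section 20 an annual committee review that can recommend modification or termination, Section 18.4 termination at any time for safety, and the network-site instructions a possible-DLT memo and regular teleconferences. Five grade 4 or 5 events would pass through all of these. What they lack is a threshold. At dose level -1, the one-third sentence in Section 9.1 is not limited to six patients and, read literally, could act as a stop in an expansion there.
- A reader might infer that the fifth DLT is final in every case. That holds for the rule as written, with n = 12, but Sections 9.2 and 19.5.1 leave the denominator open.

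**Conclusion.** The point holds for dose level 1 as the absence of a prespecified numeric accrual stop in the expansion, not as an absence of safety oversight. With 12 in the denominator, the fifth DLT settles the Section 19.1 verdict and nothing numeric follows from it. The benefit of a stop is moderate once the expansion is open (about 1.4 to 3.8 patients on average at true rates of 0.40 to 0.60, or 0.6 to 2.1 with two already enrolled) and small from study start (about 0.16 to 0.33 patients with no lag). These sizes rest on independent outcomes, a common DLT rate and the stated lags. The change is still worth making: it uses the plan's own boundary and leaves the probability of accepting the regimen as it is.

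**What to change.** In Sections 9.1 and 19.1, add: accrual to the expansion cohort is suspended once the fifth DLT among expansion patients is confirmed, because the Section 19.1 criterion is then met. Have the existing weekly AE review keep the running count, and point the Section 6 reference to this sentence. In the same edit, define which 12 patients form the DLT denominator, reconciling the replacement rule in Section 9.2 with the toxicity-evaluable definition in Section 19.5.1; otherwise the trigger and the final analysis could disagree. The sentence concerns accrual only and does not address the care of patients already on treatment.

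The cost arises only if the stop is triggered: the DLT rate is estimated from fewer patients, and fewer pre/post pairs are available for the Wilcoxon analysis in Section 19.4, whose power statement assumes 18.
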